finding of a lung nodule. This alert will set in motion an automated process that will notify the patient and the ordering provider about the CT findings and the study. The patients will thus be passively enrolled in the trial (i.e. we will ascertain outcomes of interest by reviewing electronic health records over the follow up period. Other than accessing their records, and inviting them to complete a survey describing their experiences, there is no planned change in the care they receive.) They will be notified that they have been included in the study, told what the study entails (i.e. following the course of their care) and they will be provided with information on how to opt out of the study and thus not have any of their information included in our analysis should they choose. Any subjects who choose to opt out will have all of their data removed from the study archives. Subjects will have the opportunity to opt out when they receive the invitation to complete surveys of patient-reported outcomes. We do not anticipate accrual issues. After a discussion with our patient partners we believe the majority of patients will agree to participate because of the “standard of care” nature of this study therefore a recruitment plan will not be devised. However, if underperforming sites are identified, a site - specific recruitment plan will be devised, implemented and monitored.

Each participating institution must obtain IRB approval to conduct this study. Sites will request an institutional waiver of consent. Obtaining individual patient consent is not possible, because there is no opportunity to contact the patient in between the time that the nodule has been identified by the interpreting radiologist and the time that the intervention is delivered (in the form of recommendations for surveillance that will be embedded in the formal radiology report). In addition, receipt of care at a participating site should not pose any additional risks to patients, since both options for surveillance are based on guidelines and consistent with current standards of care. Recent papers have argued that the greater risk to patients is not to perform the study of comparative effectiveness, because the risks associated with participating in the study might be very small.

All subjects (including physicians) will receive written communication describing the purpose of the study, study procedures, and the risks and benefits of participating in the study. If additional information about the study is needed the study coordinator and/or local PI can be contacted. No subject will be included in the study against his or her will. Subjects also have the right to withdraw from the study at any time.

Protections Against Risk

All investigators and research staff at participating sites will be required to maintain up-to-date training in human subject protection and good clinical practice through *Collaborative Institutional Training Initiative (CITI; <https://www.citiprogram.org/default.asp>)* and HIPAA training. To protect subjects from a breach in confidentiality of personal health information, all data will be stored on secure servers that are password protected. Access to the database will be granted to as few as possible with a need to know. Additional security precautions include encryption, digital certification, audit logs, and firewall protection. Unique study-specific identifiers will be assigned to support accurate linkage of data on the same individual across time frames and data files. Encrypted data will be transferred from participating sites to the UC Davis central database using a web-based secure file transfer site and servers. This method is commonly used.

State cancer registries are experienced with data linkage procedures. Sites will send identifiers to the UC Davis Data Coordinating Center, who in turn will link these data with the cancer registries. The state cancer registries will do the linkages, determine who developed cancer, and provide relevant information to the data coordinating center, stripped of personal identifiers except the study identification number. All transfer of identifiers and cancer information will be through appropriate encrypted means following established data transfer protocols of each participating institution and cancer registry. The cancer registry will destroy files with personal health information after they are no longer deemed of use for the project.

The Data Safety Monitoring Board (DSMB) employed for this study will provide another layer of protection. The DSMB will meet twice each year by conference call to review unanticipated adverse events. When data are presented or published, subjects will not be individually identified.

Potential Benefits of the Proposed Research to Human Subjects and Others

Given patients will receive similar care whether or not they participate in the study, there will be no direct benefit of participation. There is no direct benefit for physicians participating in the surveys. The benefit for subjects and physicians is in the knowledge gained to improve evidenced based health care.

This study follows standard practices with minimal additional risks. Although there is no direct benefit to the subjects or physicians contributing data the new knowledge derived is anticipated to have a substantial impact on overall health care.

Importance of the Knowledge to be Gained

Lung cancer is the leading cause of cancer deaths worldwide for both men and women. One reason for the poor outcomes is the lack of a screening and early detection tool. As a consequence, patients are typically diagnosed with late stage disease for which there is no cure. Recently, low dose CT was shown to detect early stage lung cancer with a significant decrease in lung cancer mortality. However small pulmonary nodules detected on CT are problematic because they are infrequently cancerous, and the benefits of intensive testing to identify cancer must be balanced by considering the harms of unnecessary testing in patients with nodules that are benign. Several guidelines have been developed to make recommendations for the evaluation of small pulmonary nodules, but the evidence supporting them is limited. Moreover adherence to guidelines is highly variable. At the completion of this

study we will have empirical data to support an evidence-based guideline for the surveillance of small pulmonary nodules.

The adoption of a standard guideline for the evaluation of small pulmonary nodules that can immediately impact the lives of millions of at risk subjects justifies the minimal risk participants in this trial may experience. Subjects can be reassured that since the trial follows clinically accepted practice, was designed with patient input, and has a data and safety monitoring plan, every effort is being made to minimize risk.

Data and safety monitoring plan

An independent data and safety monitoring committee and plan will be created for this trial. In addition, each participating institution must abide by their institutional data and safety monitoring guidelines. The site PI is responsible for ensuring adherence to all local, state and federal guidelines.

Clinical Trials.gov Requirements

This trial has been registered with ClinicalTrials.gov.

Inclusion of Women and Minorities

1. Describe the planned distribution of subjects

The distribution of subjects by sex/gender, race and ethnicity is provided in the accompanied enrollment table (**Table 6**).

Table 6: Distribution of subjects by sex/gender, race and ethnicity			
Ethnic Category	Females	Males	Total
Hispanic or Latino	2,990	2,894	5,884
Not Hispanic or Latino	14,842	14,374	29,216
Ethnic Category: Total of All Subjects *	17,882	17,318	35,200
Racial Categories			
American Indian/Alaska Native	214	208	422
Asian	948	918	1,866
Native Hawaiian or Other Pacific Islander	36	34	70
Black or African American	2,360	2,286	4,646
White	14,323	13,872	28,195
Racial Categories: Total of All Subjects *	17,882	17,318	35,200

* The “Ethnic Category: Total of All Subjects” must be equal to the “Racial Categories: Total of All Subjects.”

The distribution is based on the general population in the United States using the 2013 Census Data. The sample size calculation is based on the estimated 35,200 subjects projected to have a small pulmonary nodule(s) on a chest CT.

2. Describe the subject selection criteria and rationale

Subjects selected to participate in this study is based on a chest CT finding of a small pulmonary nodule and not on the basis of sex/gender or racial/ethnic group. To the best of our knowledge there is no data to suggest that sex/gender or racial/ethnic group influences the incidence of small pulmonary nodules.

3. Provide a compelling rationale for exclusion of any sex/gender, racial, or ethnic group

There is no exclusion of subjects based on sex/gender, racial or ethnic group.

4. Describe proposed outreach programs for recruiting sex/gender, racial and ethnic group members as subjects.

Each participating institution will be responsible for developing an outreach program if a current program does not exist to ensure enrolled subjects match their catchment region. If gaps in sex/gender and/or racial/ethnic enrollment are identified an action plan will be designed, executed, monitored and revised as needed. Trial demographics will be a standing agenda item on the steering committee conference calls.

NIH-Defined Phase III Clinical Trial Requirements

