Lung cancer remains the number one cause of cancer death for both men and women in the United States,²⁷ killing more Americans each year than breast, prostate and colorectal cancer combined. Because most patients with lung cancer present with symptomatic, advanced disease, only 18% of lung cancer patients are still alive 5 years after diagnosis.²⁷ In contrast, lung cancer is often curable when it presents as an asymptomatic nodule, with 5-year survival rates of 55% to 80%.¹⁹ However, up to 59% of patients who undergo resection for suspected cancer ultimately prove to have a benign nodule.²⁸⁻³²

A related concern is that an unknown number of patients with malignant nodules might miss opportunities for cure because diagnosis and treatment are delayed during the period of CT surveillance. Practice variation is another issue. In a prior study of evaluation practices for veterans with pulmonary nodules based on chart review, we found that almost 30% received less intensive care than recommended and 20% received more care than recommended, indicating substantial room for improvement.²⁴

Lung cancer and lung nodules are understudied compared with other conditions that lead to comparable morbidity and mortality. This pragmatic, cluster-randomized trial of comparative effectiveness will be integrated into routine clinical practice in diverse settings so that the results will be broadly generalizable.

Patient-centeredness:

This study is patient-centered because it fills an unmet need for information that is critically important for informed shared decision-making by patients and clinicians. To further ensure patient centeredness, we engaged our patient and stakeholder team when developing this proposal to identify and prioritize patient-centered outcomes of greatest importance. Patients and stakeholders selected “cure of cancer” as the most important priority, and endorsed our

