Participants taking Internet surveys will provide informed consent and complete the REDCap-enabled surveys in the language of their choice, English or Spanish. Participants will be surveyed at approximately 1-2 and 13-24 months after enrollment, and at the end of surveillance.

To complement the patient perspective, we will also design a brief survey to capture provider satisfaction with the assigned protocol for surveillance and their perception about barriers to its implementation. Development of the brief physician survey will be led by [name] at UCSF, based on her ongoing qualitative pilot study of physician attitudes and beliefs about cancer screening.^{57,58} The survey will primarily focus on radiologists and ordering providers (pulmonologists and thoracic surgeons) at each study site, because they are most directly involved with lung nodule evaluation, although we will explore the possibility of surveying primary care providers. Surveys will be distributed to radiologists and ordering providers at the start of the trial and near the end of the study enrollment period (approximately mid-way through the trial).

Aim 3 Outcomes, Nodule-Related Resource Utilization and Radiation Exposure: We will compare health care resource utilization between groups by conducting searches of structured data in EHRs for relevant ICD-9 procedure codes that appear during the surveillance period (from date of the index CT scan to the date of first cancer treatment or 2 years of follow-up, whichever comes first). Most study sites use the Epic EHR, which allows for efficient searching of utilization tables; other EHR systems have similar capabilities. We will capture all relevant imaging tests (chest CT, PET,), invasive biopsy procedures (bronchoscopy, transthoracic

needle biopsy), thoracic surgical procedures, outpatient visits, emergency department visits and hospitalizations, as we have done previously for the NCI and VA-funded CanCORS study.⁵⁹ We will also record procedure-related complications by searching for diagnostic codes for pneumothorax, respiratory failure and major bleeding (relying in part on operational definitions created by the Agency for Healthcare Research & Quality Patient Safety Indicators).⁶⁰

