that went into effect in 2013, CTDIvol and DLP must be reported in the radiology report and will be extracted from the electronic medical records. Because each site has developed their own technique for reporting the radiation dose metrics in the medical record, the technique for extracting these data will be locally determined. Effective dose, measured in milli-Sieverts (mSv), combines information about the radiation imparted to the patient, the scan location reflecting the organs irradiated, and the deleterious effect, primarily of developing cancer in the future. Effective dose increases with the dose length product and is a function of the radio-sensitivity of the tissues irradiated. Effective dose will be calculated from the DLP for each examination using existing established conversion formulas, and summed over the study period for each enrollee.

Aim 4 Outcomes, Patient and Provider Adherence: We will measure adherence to the assigned surveillance protocol at the level of the interpreting radiologist, the ordering provider, and the individual patient. First, we will measure adherence with each recommended surveillance test: was the test recommended by the radiologist, ordered by the provider, and completed by the patient? Adherence at the patient and provider levels can be extracted from structured data in the EHR. To measure adherence at the level of the interpreting radiologist, we will review a sample of radiology transcripts to determine whether the recommendation for surveillance were present and per protocol. These analyses will provide granular information about adherence on a test-by-test basis and pinpoint the level of non-adherence. In addition, we will measure overall adherence, defined as completion of all recommended tests for surveillance at the individual patient level.

Data Management

The Data Coordinating Center (DCC) at UC Davis will be the central location for data management. The DCC will collect data captured locally at each participating site. This collected

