The primary study objectives include, among individuals with small pulmonary nodules identified either incidentally or by screening, comparing more vs. less intensive CT surveillance for the progression of cancer beyond AJCC 7th edition stage T1a disease (or T1b in the AJCC 8th edition) (Aim 1), nodule-related emotional distress (Aim 2), health care resource utilization and exposure to diagnostic radiation (Aim 3), and overall adherence with the recommended surveillance protocol (Aim 4).

The secondary objectives include comparing more vs. less intensive CT surveillance for the timeliness of lung cancer diagnosis and overall survival of patients in each study arm who prove to have a cancerous nodule (Aim 1), patient general health status and satisfaction with the evaluation process and the provider satisfaction with the surveillance protocol and the evaluation process (Aim 2), and adherence to use of low radiation-dose techniques (Aim 4). In general, we hypothesize that more intensive follow-up will result in more CT imaging (by design), greater radiation exposure, more downstream testing, greater anxiety and emotional distress, slightly shorter times to cancer diagnosis, and worse adherence to follow-up, and no effect on cancer stage distribution or overall survival.

Primary endpoints:

Aim 1: Proportion of lung cancers that are greater than 20mm

- Measured as progression beyond AJCC 7th edition T stage of T1a or, equivalently, AJCC 8th edition T stage of T1b

Aim 2: Nodule-related anxiety and emotional distress at 1-2 months, 13-24 months, and ≥25 months after nodule identification

- Measured using the IES-R and STAI-6

Aim 3:

1. Health care resource utilization within 26 months following nodule identification
 - Number of visits within 26 months of nodule identification, including the following exams (separate analyses by type of exam):
 - Chest CT scans
 - Chest x-rays
 - PET or PET/CT scans
 - Biopsies (look separately and together): Bronchoscopic biopsy, percutaneous biopsy, surgical biopsy/resection, extrapulmonary biopsy.
 - We will not include any exams after the date of cancer diagnosis, but will include biopsy that led to the cancer diagnosis
2. Serious complications within 7 days and within 30 days of a chest CT, chest x-ray, PET or PET/CT scan, or biopsy (bronchoscopic biopsy, percutaneous biopsy, surgical biopsy/resection, extrapulmonary biopsy) performed within 26 months of baseline CT:
 - Pneumothorax

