Appendix C: Surveillance Protocols

Table C1: Surveillance protocol for incidental nodules, Group A, more intensive surveillance

Patient and Nodule characteristics		Surveillance times (months from index CT)
Solid, with Risk Factors		
≤4		12
>4 to ≤6		6, 18
>6 to ≤8		3, 9, 21 to 24
>8		3, 9, 21 to 24 or PET or tissue
Solid, without Risk Factors		
≤4		Optional (12)
>4 to ≤5		12
>5 to ≤8		6, 18
>8		3, 9, 21 to 24 or PET or tissue
Part-solid		
Solitary, solid component ≤5		3, 15, 27, 39
Solitary, solid component >5		3, tissue if persists
Multiple, solid component ≤5		3, 15, 27, 39
Multiple, solid component >5		3, tissue if persists and solid ≥5
Non-solid		
≤5, solitary		None
>5, solitary		3, 15, 27, 39
≤5, multiple		24, 48
>5, multiple		3, 15, 27, 39

Table C2: Surveillance protocol for incidental nodules, Group B, Less intensive surveillance

Nodule characteristics	Surveillance times (months from index CT)
Solid	
<6, solitary or multiple	None (Optional at 12 months in patients with risk factors)
≥6 to ≤8, solitary	12, 24
≥6 to ≤8, multiple	6, 18
>8, solitary or multiple	3, 15, 27 or PET or tissue
Part-solid	
<6, solitary	None
<6, multiple	6, 24, 48
≥6, solid component <6	6, 18, 30, 42, 54, 66
≥6, solid component ≥6	6, tissue if persists
Non-solid	
<6, solitary	None
≥6, solitary	12, 36, 60
<6, multiple	6, 24, 48
≥6, multiple	6, 24, 48

Table C3: Surveillance protocols for screening-detected nodules

Lung-RADS Category	Nodule characteristics	Surveillance times (months from index CT)		
		Group A	Group B	
1	No nodule	12, 24...	12, 24...	
	Calcified nodule			
	Fat-containing nodule			
2	Solid nodule <4	12, 24...	12, 24...	
	Solid nodule <6	6, 18, 30...		
	New solid nodule <4			
	Part-solid nodule <6			
	Non-solid nodule <20			
	Non-solid nodule ≥20, unchanged or slow-growing			
	Category 3 or 4 nodule unchanged for >3 months			
3	Solid nodule ≥6 to <8	3, 15, 27...	6, 18, 30...	
	New solid nodule, ≥4 to <6			
	Part-solid nodule ≥6, with solid component <6			
	Part-solid nodule, new <6			
	Non-solid nodule ≥20			
4A	Solid nodule ≥8 to <15	3, 9, 21... (PET may be used when solid component ≥8)	3, 15, 27... (PET may be used when solid component ≥8)	
	Solid nodule, new ≥6 to <8, or growing <8			
	Part-solid nodule ≥6, with solid component ≥6 to <8			
	Part-solid nodule, new or growing, with solid component <4			
	Endobronchial nodule			
4B	Solid nodule ≥15	CT at 3 months, PET or tissue, depending on probability of cancer and comorbidities		

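### Full-protocol patient adherence (Aim 4) counts patients with no scan due as adherent, a group larger by design in the less intensive arm, and sets no end date for scoring

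*Combined protocol and SAP*

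**What the plan says.** The section on Aim 4 outcomes first plans a test-by-test measure (recommended, ordered, completed) and then adds the summary measure: "In addition, we will measure overall adherence, defined as completion of all recommended tests for surveillance at the individual patient level". The Primary endpoints list for Aim 4 includes adherence to the first recommended exam and to the full protocol. H4 predicts worse adherence in the more intensive arm among all participants with a nodule of 15 mm or less. The Analysis Plan tests a binary indicator by hierarchical logistic regression, with and without adjustment for nodule size and other factors. The power section assumes 16,000 patients per group, 27% non-adherence in the more intensive arm and an ICC of 0.01, and claims 90% power for a 5.9-point improvement. Table 4 adds only that imaging is to be checked as completed per protocol.

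Appendix C gives some patients nothing to complete. For solid nodules under 6 mm in Group B, Table C2 reads "None (Optional at 12 months in patients with risk factors". For solid nodules above 8 mm, Group A has "3, 9, 21 to 24 or PET or tissue" and Group B has "3, 15, 27 or PET or tissue". Screening schedules in Table C3 are open-ended in both arms, for example "3, 9, 21... (PET may be used when solid component ≥8".

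Aim 3 has time limits: "Health care resource utilization within 26 months following nodule identification" in the endpoint list, and "from date of the index CT scan to the date of first cancer treatment or 2 years of follow-up, whichever comes first" in the Aim 3 outcomes section. Aim 4 has none. The sample-size section promises follow-up of at least two years.

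**The concern.** An all-or-none measure taken in everyone mixes two things: whether patients do what is asked, and how much is asked. At the extreme, a patient asked for nothing passes automatically. If the protocols put different shares of otherwise similar patients in that position, the arms differ on a primary Aim 4 endpoint even when patients behave identically. Adjusting for nodule size does not help, because within a size band it is the arm that decides whether anything is due.

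The missing end date is a second gap. Some listed scans fall after the follow-up that every patient is sure to have, and the plan does not say whether they count.

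The gap reaches two other places. First-exam adherence is undefined for a patient with no exam due. The on-treatment sensitivity analyses of the primary cancer-stage outcome select patients by the same adherence definition. The radiologist-level measure is not affected.

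**Working it through.** **1. Reproduce the plan's power.** Inputs from the power section: 16,000 per arm, 27% non-adherent, 5.9-point improvement (27% against 21.1%), ICC 0.01, two-sided 0.05. The documents give 24 randomised sites; 12 equal clusters per arm is assumed.
- Cluster size m = 16,000/12 = 1,333.
- Design effect = 1 + (1,333 − 1) × 0.01 = 14.3.
- Effective n = 16,000/14.3 ≈ 1,117 per arm.
- SE = √[(0.27 × 0.73 + 0.211 × 0.789)/1,117] = 1.80 points.
- Power = Φ(5.9/1.80 − 1.96) = 90.5%. The stated 90% is reproduced.

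**2. Who has no required scan (incidental nodules, Tables C1 and C2).**

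| Category | Group A | Group B |
|---|---|---|
| Solid ≤4 mm, no risk factors | optional only | none |
| Solitary non-solid ≤5 mm | none | none |
| Solid <6 mm, risk factors | scan due | optional only |
| Solid >4 to <6 mm, no risk factors | scan due | none |
| Solitary part-solid <6 mm | scan due | none |
| Solitary non-solid >5 to <6 mm | scan due | none |

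Every category without a required scan in Group A also lacks one in Group B, and Group B adds four. The set is strictly larger in Group B. Table C3 lists no screening category without a scan, so this part concerns incidental nodules.

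**3. Size of the shift under the literal rule.** Let a be the share with nothing required in both arms, s the extra share in Group B, and 73% the adherence among patients with a scan due, equal in both arms.
- Group A adherence = a + (1 − a) × 0.73.
- Group B adherence = (a + s) + (1 − a − s) × 0.73.
- Difference, B minus A = s − 0.73s = 0.27s; a cancels.

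The documents do not give s. Over an assumed range, with the effective n from step 1 and a = 0 for the standard error:

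| s | Shift toward H4 | Chance of a significant result for H4 with no difference in behaviour |
|---|---|---|
| 5% | 1.4 points | 0.11 |
| 10% | 2.7 points | 0.31 |
| 20% | 5.4 points | 0.85 |

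The shift alone would equal the powered 5.9 points at s = 0.059/0.27 ≈ 22%.

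**4. Late scans.** Table C1 lists scans to month 39 for several subsolid categories and to month 48 for small multiple non-solid nodules. Table C2 runs to month 66 for part-solid nodules ≥6 mm with a solid component <6 mm. For solid nodules above 8 mm, only Group B has a scan after month 24 (month 27, against 21 to 24). The net effect depends on how long each patient is observed and on case mix. The documents fix neither, so no figure is given.

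**5. What a common window leaves behind.** By month 24, solid >8 mm has three scans due in Group A and two in Group B. If each scan is completed with probability 0.90 (assumed, independent, equal in both arms), all-or-none adherence is 0.90³ = 73% against 0.90² = 81%. That is about 8 points toward H4 with no difference per scan. Solid >6 to 8 mm with risk factors (solitary in Group B) also has three against two, and solitary non-solid ≥6 mm has two against one. Multiple non-solid ≤5 mm goes the other way, one against two.

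**The case against.** Several counter-arguments have force.

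- **The share s is unknown.** True; every size above is conditional on it. The direction is not, because it follows from Tables C1 and C2 together with the literal definition.
- **All recommended tests may mean those recommended for that patient.** The outcome section asks whether the radiologist recommended each test, and report templates can be tailored. That would settle the optional scans, and the fix adopts it. It does not settle patients for whom nothing is recommended.
- **Adherence is descriptive.** The pragmatic-trial scoring list under Research Design and Methodology says so for participants. Yet the endpoint list makes it primary for Aim 4, and it has a directional hypothesis and a power calculation.
- **A simpler protocol is meant to be easier to follow.** The Background says this, and it justifies keeping the all-participant figure. It does not justify reading that figure as behaviour.
- **Details may sit in the data dictionary or manual of procedures.** Possible; they are not among the documents reviewed. Aim 3's two-year period could also be extended to Aim 4, but nothing says that it is.

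Two stronger readings are tempting and are not supported. A reader might infer that the scoring choice can reverse the result. That rests mainly on scoring patients with nothing due as non-adherent, which the definition does not suggest. Without that rule, the assumed range gives shifts from 0 (such patients excluded) to 5.4 points toward H4. A reader might also infer that late scans push the result against H4, mainly through solid nodules above 8 mm. That needs data to stop near month 24 to 26 for everyone, whereas the plan promises at least two years after a 28-month enrolment period.

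**Conclusion.** The concern holds in a limited form. As written, full-protocol adherence favours the less intensive arm by construction, by 0.27 × s under equal behaviour. The 0.27 is the plan's assumed non-adherence, applied here to patients with a scan due; s must come from the trial's own nodule mix. At the assumed values the shift is 1.4 to 5.4 points, below the powered 5.9 but large enough at s = 20% to give a significant result 85% of the time with no difference in behaviour. The absence of a scoring window is a real gap, but its size and net direction are not established. Effects on ordering-provider adherence and on the on-treatment analyses are possible and unquantified. The plan's power figure is not in error. The change should be made, with medium confidence in its practical importance; the primary intention-to-treat analysis of cancer stage is untouched.

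**What to change.** Amend the Aim 4 section and the H4 analysis as follows.

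1. Compare patient-level first-exam and full-protocol adherence among nodule categories with at least one non-optional scan due in both arms.
2. Count an optional scan only if it was recommended for that patient.
3. Score only scans whose due date plus a stated grace period falls in one common window. Aim 3's 26 months is a candidate (due by month 24 plus two months), provided data are held that long for all participants. Censor at death, cancer diagnosis or loss to follow-up.
4. State how a patient who takes the listed PET or tissue alternative is scored.
5. Make adherence per scan due, which the plan already intends to measure, the main between-arm contrast, because the all-or-none measure still favours the arm with fewer scans (step 5 of the working).
6. Report the all-participant figure and the no-scan and optional-only categories alongside.
7. Use the same definition in the on-treatment analyses.

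Table 3 lists scans to month 30, and Table C2 to month 66, for Group B part-solid nodules ≥6 mm with a solid component <6 mm. The two must be reconciled before scoring.

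The cost is SAP wording, some recoding of existing EHR data and a smaller denominator. Clustering dominates the variance, so little precision is lost. With 12 clusters per arm and ICC 0.01, the difference detectable with 90% power goes from about 5.9 points at 16,000 per arm to 6.0 at 8,000 (design effect 7.7) and 6.4 at 4,000 (design effect 4.3).
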